15.2 SUBJECT DIARY FOR ASSESSMENT OF LOCAL TOLERABILITY AND SOLICITED AEs

The subjects will be provided with an electronic diary and will be asked to record the presence of any administration site reactions (pain or pruritus) for 10 days starting in the evening the day after each treatment.

In addition, the subjects will be asked to record the occurrence of solicited AEs (fever [temperature >38°C], chills, sweating, tiredness, headache, muscle aches (not associated with the administration area), joint pain (not associated with the administration area), runny nose, nasal congestion, sneezing, cough, sore throat and nausea for 10 days starting in the evening the day after each treatment.

All reactions will be classified as none, mild, moderate or severe by the subjects. The duration of each reaction (hours) will also be recorded. Reactions classified as moderate or severe will be reported as AEs.

The diary will also contain a question as to whether the subject has taken any antipyretic medication or any other type of medication to treat the recorded symptoms. Any medication taken will be recorded as a concomitant medication.

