For subjects in group 1 to 4 there will be a total of 4 visits to the clinic; Visit 1 (screening), Visit 2 (Day 0), Visit 3 (Day 21+7) and Visit 4 (Day 42+7). Telephone contacts will be taken approximately every 8th week after the last visit to the clinic (visit 4) for collection of any adverse events (AEs) of special interest or serious AEs (SAEs) that may have occurred after Visit 4 during a 6 months safety follow-up period starting from the day of the last vaccination.

Subjects in group 5 and 6 will receive treatment in an unblinded fashion via a single intramuscular (group 5) or single intranasal (group 6) administration on Day 0 (Visit 2). No treatment will be given on Day 21+7 (Visit 3).

For subjects in group 5 and 6 there will be a total of 3 visits to the clinic; Visit 1 (screening), Visit 2 (Day 0), and Visit 3 (Day 21+7). Telephone contacts will be taken approximately every 8th week after the last visit to the clinic (Visit 3) for collection of any AEs of special interest or SAEs that may have occurred after Visit 3 during a 6 month safety follow-up period starting from the day of the last vaccination.

In all groups safety and tolerability, including local tolerability, will be assessed. Local tolerability (swelling and redness [assessed by an independent evaluator] and pain and pruritus [assessed by the subject]) will be assessed before and after each treatment (Visit 2 and 3 for group 1 to 4 and Visit 2 for group 5 to 6). Safety and tolerability will be assessed by vital signs (blood pressure and heart rate), physical examination, 12-lead electrocardiogram (ECG), collection of AEs and laboratory tests (haematology, clinical chemistry and urinalysis). Subjects with suspected influenza will be tested to confirm presence and strain of the influenza virus.

Local tolerability will also be assessed by the subjects' recording of the presence or absence of local administration site reactions (pain and pruritus) and solicited AEs (runny nose, nasal congestion, sneezing, fever [temperature >38°C], chills, sweating, headache, tiredness, muscle aches, joint pain, cough, sore throat, nausea) in an electronic diary for 10 days after each dosing occasion, starting in the evening the day after treatment.

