Immune responses against the vaccine antigens will be evaluated in both nasal and blood samples. Influenza-specific immune responses will be evaluated in nasal samples (IgA) and in serum (HI and VN) and PMBC (T cells) from blood samples. Blood samples for peripheral blood mononuclear cell (PBMC) preparation and subsequent T-cell analysis will be taken from 10 subjects per group.

The total study duration for the subjects in the study will be up to 36 weeks (group 1 to 4) and 33 weeks (group 5 and 6) including a 6 week screening period and a 6 months follow-up period after the last dose.

Number of Patients

Approximately 243 subjects will be screened in order to randomise 162 subjects to 6 treatment groups in a ratio of 2:2:2:1:1:1.

Objectives**Primary Objective**

To evaluate the safety and tolerability of Immunose™ FLU based on Endocine™ and quadrivalent influenza antigen.

Secondary Objective

To evaluate the immune response to Immunose™ FLU based on Endocine™ and quadrivalent influenza antigen by measurement of haemagglutination-inhibition (HI) and virus neutralization (VN) titres.

Exploratory Objective

To evaluate the immune response to Immunose™ FLU based on Endocine™ and quadrivalent influenza antigen by measurement of immunoglobulin A (IgA) in nasal secretions.

Primary Endpoints

- Type and incidence of AEs and SAEs from the time of first study drug administration (Visit 2) until the last visit to the clinic (Visit 4 for group 1 to 4 and Visit 3 for group 5 to 6).
- Type and incidence of SAEs and AEs of special interest during the 6 months safety follow-up.
- Frequency and severity of administration-site reactions as assessed by an independent evaluator with help from the study subject before study drug administration and 15 minutes and 120 minutes after study drug administration. Administration-site reactions to be recorded are swelling, redness, pain and pruritus in the administration area (nose or arm). Reactions are classified as none, mild, moderate or severe. The administration-site reactions pain and pruritus will also be recorded by the subject in an electronic diary for 10 days starting in the evening the day after each treatment and classified as none, mild, moderate or severe.

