Administration site reactions will be collected at the clinic during 2 hours of observation after each study drug administration. In previous studies with Endocine products such reactions, if occurring, were transient and in the vast majority of cases disappeared within this time period. Possible later local and systemic reactions will be collected over 10 days using a diary. In accordance with the guidelines on influenza vaccines and adjuvanted vaccines a long-term safety follow-up for 6 months after the last vaccination is included to detect any potential late occurring immune-mediated diseases (IMDs) that may be associated with the vaccination.

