Pregnancy test (urine dipstick) ³	X ³	X ³				
HIV, Hepatitis B and C blood sampling	X					
Urine drug screen	X					
Haematology and clinical chemistry blood sampling	X		X			
Urinalysis sampling	X		X			
Prior and concomitant medications	X	X	X			
Randomisation		X				
Diary instructions		X				
Diary check-up						
AEs ^{4,5}		X ⁴	X			
Vital signs ⁶	X	X ⁵	X	X ⁵	X ⁵	X ⁵
Nasal swab ⁷	X	X ⁶	X ⁶			
Immunology blood sampling ⁸		X ⁸	X ⁸			
Administration site inspection for local tolerability ⁹		X ⁹				
Dose administration ¹⁰		X ¹⁰				

¹ At least 3 weeks between Visit 2 and Visit 3.

² Continued eligibility criteria are defined in Section 12.6.

³ Pregnancy test should be performed in females at screening and pre-dose at Visit 2.

- ⁴ Pre-treatment events will be collected from signing of the ICF until first dose and AEs will be collected post study drug administration.
- ⁵ SAEs and AEs of special interest (Section 14.1.5).
- ⁶ Recording of vital signs (heart rate and blood pressure) should be performed prior to dosing and at 30 minutes and 120 minutes post study drug administration (before the subject leaves the clinic). Temperature should be measured prior to each dosing occasion.
- ⁷ Nasal swab for IgA analysis according to specific instructions (Section 16.1).
- ⁸ Blood sampling for serum from all subjects and blood sampling for PBMC preparation and T-cell analysis as randomized (10 subjects per group)
- ⁹ Assessment of local tolerability parameters should be performed prior to dosing and at 15 and 120 minutes post-study drug administration according to specific instructions (Section 15.1).
- ¹⁰ Nasal or intramuscular study drug administration according to the manufacturers' instructions.

Table 4 Timing of assessments on treatment day group 5 and 6

Time point	Assessment	Visit 2	Comment
Pre-dose	Continued eligibility criteria	X ¹	
	Pregnancy test (urine dipstick)	X ¹	
	Vital signs including body temperature	X ¹	
	Concomitant medications	X ¹	
	Pre-treatment events	X	
	Randomisation	X	
	Immunology blood sampling	X	
	Local tolerability assessments	X ²	By independent evaluator ²
0	Dose administration	X	
15 min +5min	Local tolerability assessments	X ²	By independent evaluator ²
30 min ±5 min	Vital signs	X	
120 min ±5 min	Local tolerability assessments	X ²	By independent evaluator ² Timing of local tolerability assessment is prioritised over timing of vital signs assessments
120 min ±20 min³	Vital signs	X ³	
Post-dose	AEs	X	
	Diary hand-out and instructions	X	

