13.8 ASSESSMENT OF TREATMENT COMPLIANCE

Following administration, the site personnel should evaluate whether the administration was successful or not (Y/N). Dripping, sneezing and swallowing in association with the administration must be commented on in the eCRF.

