- Recording of vital signs at 30 minutes and approximately 120 minutes post study drug administration (before the subject leaves the clinic).
- AE collection.
- Diary instructions for daily AE recording during 10 days starting in the evening the day after treatment.

14.1.3 Visit 3

The activities and assessments to be performed at Visit 3 are outlined below. A re-assessment of eligibility will be made prior to dosing, see Section 12.6. For details on the timing of each assessment, refer to Table 1, Table 2 and Table 3.

14.1.3.1 Visit 3 group 1 to 4

The following activities and assessments will be performed **pre-dose**:

- Pregnancy test (females only, urine dipstick).
- Review of diary since the previous visit.
- AE collection.
- Recording of concomitant medication.
- Recording of vital signs (heart rate, blood pressure and body temperature).
- Nasal swab for nasal IgA sampling (at least 60 minutes before assessment of the pre-dose assessment of local tolerability).
- Blood sampling for immunology analyses.
- Inspection of nasal cavities and recording of local tolerability parameters.

Nasal **study drug administration** will be performed as summarized in Section 13.5.1.

The following activities and assessments will be performed **post-dose**:

- Recording of local tolerability parameters at 15 and 120 minutes post study drug administration.
- Recording of vital signs at 30 minutes and approximately 120 minutes post study drug administration.
- AE collection.
- Diary instructions for daily AE recording during 10 days starting in the evening the day after treatment.

14.1.3.2 Visit 3 group 5 and 6

The following activities and assessments will be performed:

- Review of diary since the previous visit.

- AE collection.
- Recording of concomitant medication.
- Recording of vital signs (heart rate and blood pressure).
- 12-lead ECG.
- Physical examination.
- Urine sampling of urinalysis parameters.
- Blood sampling for assessment of haematology and clinical chemistry parameters. Fasting is not required.
- Nasal swab for nasal IgA analysis.
- Blood sampling for immunology analyses.

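### The solicited-AE endpoint covers the ten days after dosing, but its diary starts the next evening and the period of the first entry is not stated

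*Combined protocol and SAP*

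**What the plan says.** The frequency of solicited AEs is one of the primary endpoints (synopsis; Section 10.1.1). That bullet has subjects recording symptoms over the ten days following administration and mentions no delayed start.

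The collection rule is different. Section 15.2 has the diary completed "for 10 days starting in the evening the day after each treatment", both for site pain and pruritus and for the 13 solicited AEs. The synopsis and Section 11 say "in an electronic diary for 10 days after each dosing occasion, starting in the evening the day after treatment". The visit procedures in Sections 14.1.2 and 14.1.3.1 give "Diary instructions for daily AE recording during 10 days starting in the evening the day after treatment". No section states the period that an entry covers. Section 15.2 adds: "The duration of each reaction (hours) will also be recorded. Reactions classified as moderate or severe will be reported as AEs".

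Section 9.5 explains the division of labour. Site reactions are watched in the clinic for two hours, and "Possible later local and systemic reactions will be collected over 10 days using a diary". The clinic ratings at 15 and 120 minutes cover swelling, redness, pain and pruritus (Section 15.1). Temperature is scheduled before dosing only (Table 1 footnote; Table 2). Section 18.5.2.3 builds the solicited-AE summary from what subjects record.

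**The concern.** The endpoint window appears to open at dosing, while the instrument that fills it is first completed the following evening with no instruction on how far back to look. Two subjects with the same runny nose on the afternoon of dosing could answer differently, and both would be following the protocol.

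This bears on the main purpose of the trial. Safety and tolerability are the primary objective, and Section 18.2 treats the effect of Endocine against no Endocine on tolerability as a key question. Section 9.5 reports that local symptoms were more frequent with Endocine in an earlier nasal influenza study and reversed quickly. If short early symptoms drop out of the solicited-AE table, the incidence in that table is too low, and absolute differences between groups may shrink with it.

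**Working it through.** The plan gives no figure to reproduce here. The check compares the sections and then works out the timing.

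**1. What is itemised before the first diary entry**
- Solicited AEs (Section 10.1.1): runny nose, nasal congestion, sneezing, fever, chills, sweating, headache, tiredness, muscle aches, joint pain, cough, sore throat, nausea = 13.
- Clinic checklist (Section 15.1): swelling, redness, pain, pruritus = 4.
- Items in common: 0 of 13. Fever has no scheduled check after dosing on that day either, because the post-dose vital signs are heart rate and blood pressure.
- Pain and pruritus are rated up to 120 minutes, so their itemised gap begins only then.

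**2. Other routes open from dosing**
- Staff observe subjects for local and systemic reactions for at least two hours (Section 9.6).
- AE collection starts with the first dose (Section 15.3.12), uses an open question (15.3.2), and accepts any untoward occurrence (15.3.1), with mild as one of the grades (15.3.7.1).
- Section 13.8 adds: "Dripping, sneezing and swallowing in association with the administration must be commented on in the eCRF". That is a compliance comment, not a symptom rating.
- The protocol describes no step that carries information from these routes into the diary-based summary.

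**3. Dosing occasions** (group sizes and doses from Table 5)
- Groups 1 to 4: (36 + 36 + 36 + 18) × 2 = 252.
- Groups 5 and 6: (18 + 18) × 1 = 36.
- Total 288, of which groups 1 to 3 contribute 108 × 2 = 216.

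**4. Time from dose to first entry.** The documents give no clock times. Assume dosing between 08:00 and 16:00 and an evening entry between 18:00 and 22:00.
- As written, shortest: 24 + 18 − 16 = 26 h. Longest: 24 + 22 − 8 = 38 h.
- With an entry on the treatment day: 18 − 16 = 2 h to 22 − 8 = 14 h.

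**5. What is left uncovered, by how far subjects look back**
- Back to dosing: nothing is uncovered, but recall spans 26 to 38 h.
- Back 24 h: coverage begins 26 − 24 = 2 h to 38 − 24 = 14 h after dosing. The first 2 h are staff-observed, which leaves 0 to 12 h seen by neither staff nor diary.

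**6. Direction of any loss (illustration; all rates assumed).** Take true incidences of 40% and 20% and the same capture in both groups.
- Capture 0.90: 36% against 18%, a difference of 18 points instead of 20.
- Capture 0.75: 30% against 15%, a difference of 15 points.
- The ratio stays at 2.0 in both cases. This shows direction only and does not estimate the loss in this trial.

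**The case against.** The best reply is that the endpoint bullet supplies the period and Section 15.2 supplies only the time of the first entry. Ten daily evening entries from Day 1 to Day 10, each covering the time since the last contact, would span exactly the ten days following administration. Asking for duration in hours also requires some looking back. The diary screens and instructions, which could settle the matter, are not among the documents. This reading is plausible and may be what is intended. However, it is not written down, and it rests on recall of 26 to 38 hours under the assumed clock times.

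A reader might go further and infer that dosing-day symptoms go uncollected, or that mild ones cannot reach the AE log because only moderate and severe reactions are passed on. The documents do not support either inference. The forwarding rule applies to reactions already rated in the clinic or the diary. General AE collection runs from dosing with no intensity threshold, so a mild early symptom that is observed or mentioned can be logged and summarised as an AE.

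Nor do the documents show that runny nose, congestion or sneezing are typically brief. Section 9.5 makes its statements on reversibility about local tolerability symptoms and administration-site reactions. It says the latter mostly cleared within the two-hour observation, when the four site items are rated. The early-nasal argument also does not apply to the 18 intramuscular doses in group 5.

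**Conclusion.** The point holds as a cheap improvement to consider. The endpoint wording and the diary start do not match, the period of the first entry is unstated, and no solicited AE is itemised before the evening after dosing at any of the 288 planned dosing occasions.

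Any loss is partial. It is confined to the diary-based solicited-AE table and concerns mainly short symptoms arising after the subject leaves the clinic. Its size cannot be derived from the documents. The hour ranges rest on the assumed clock times, and the 0 to 12 h figure also on an assumed 24-hour look-back. Safety is compared descriptively (Section 18.5.2), so no planned test is affected. The conclusion is limited to what the protocol states, since the diary itself was not available.

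**What to change.** In Sections 15.2, 14.1.2, 14.1.3.1, 11 and 10.1.1 and in the synopsis, write: *The first diary entry is made in the evening of the treatment day (Day 0) and covers all symptoms since dosing; each later entry covers the time since the previous entry, through Day 10.* Align the solicited-AE endpoint bullet in the synopsis and Section 10.1.1 with this, and check each mention of ten days against the new schedule.

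The cost is 11 entries per dose instead of 10: 288 × 11 = 3,168 against 288 × 10 = 2,880, which is 288 more (+10%). The e-diary needs minor reconfiguration, and the protocol wording must be changed through the amendment procedure in Section 19.4. No visit or symptom item is added. Diary instructions are already given after dosing on the treatment day (Table 2; in Table 4, "Diary hand-out and instructions").

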15.3 ADVERSE EVENTS

Any apparent side effects experienced by the subject will be assessed from the time the subject signs the informed consent and throughout the last visit to the clinic (Visit 4 for group 1 to 4 and Visit 3 for group 5 and 6).

The study personnel will document any pre-dose events, i.e. events reported after the signing of informed consent and before administration of the first dose in the medical history log of the eCRF.

The study personnel will document all AEs in the AE log of the eCRF, whether observed by the Investigator or spontaneously reported by the subject.

SAEs and AEs of special interest will be documented during the 6 months follow-up period starting after the last vaccination (Visit 3 or Visit 4).

The AE reporting period is described in Section 15.3.12.

15.3.1 Definition of adverse event

An AE is defined as any untoward medical occurrence in a subject who has received IMP. The occurrence does not necessarily need to have a causal relationship with the IMP. An AE can therefore be any unfavourable and unintended sign (including an abnormal laboratory finding), symptom, or disease temporally associated with the administration of IMP, whether or not causally related.

The occurrence of an AE may come to the attention of study personnel during study visits and interviews of a subject recipient presenting for medical care, or upon review by a subject monitor who is scrutinising relevant source data.

Clarifications:

Diagnostic and therapeutic non-invasive and invasive procedures, such as surgery, should not be reported as AEs. However, the medical condition for which the procedure was performed should be reported if it meets the definition of an AE. For example, an acute appendicitis that begins during the AE reporting period should be reported as "acute appendicitis" and the resulting appendectomy noticed under Comments. Pre-study conditions, which led to elective surgery during the time of the study, are not to be reported as AEs.

If an abnormal laboratory value or vital sign is associated with corresponding clinical signs and symptoms, the sign/symptom should be reported as the AE and the associated laboratory result or vital sign should be considered additional information that is to be collected in the eCRF.

15.3.2 Adverse event questioning and recording

The Investigator is to record all directly observed AEs and all AEs spontaneously reported by the subject in the subject's personal records (source data) and in the eCRFs using concise medical diagnostic terminology.

The occurrence of an AE may come to the attention of personnel during a site visit or during interview of a subject presenting for medical care. The question asked will be "Have you had any health problems since your last evaluation?". AEs may also be identified upon review by a monitor who is scrutinising relevant source data.

All AEs must be graded for:

- Seriousness (Section 15.3.3)
- Intensity (Section 15.3.7.1)
- Causality (possible relationship) to IMP (15.3.7.2)

15.3.3 Definition of serious adverse event

An AE is considered serious if it:

- results in death
- is life-threatening (this refers to an event in which the subject was at risk of death at the time of the event; it does not refer to an event that hypothetically might have caused death had it been more severe)
- requires inpatient hospitalisation or prolongation of existing hospitalisation
- results in persistent or significant disability/incapacity
- is a congenital anomaly/birth defect. The criterion congenital anomaly/birth defect in the offspring is valid for pregnancies with conception within 2 months after completion of the treatment series.
- is medically important (this refers to an event that may not be immediately life-threatening or result in death or hospitalisation, but may jeopardise the subject or may require intervention to prevent any of the SAEs defined above)

An AE is also serious if it resulted in any other medically important condition that may not result in one of the above mentioned criteria, but may still be considered serious when, based upon appropriate medical judgement, it may jeopardise the subject and may require significant medical or surgical intervention to prevent one of the outcomes listed above.

15.3.4 Definition of a serious drug reaction

The term SADR is to be used whenever either the Investigator or Sponsor or designee assessed the SAE as possibly or probably related to the IMP.

